## **Blood Pressure Screening Form**

ID: \_\_\_\_\_

Date: \_\_\_\_/\_\_\_\_/\_\_\_\_

Participant First Name: \_\_\_\_\_

Participant Last Name: \_\_\_\_\_

## **COVID-19 Screening Form**

VISIT \_\_\_\_\_

ID \_\_\_\_\_

### **Symptom Tracker:**

I need to ask about any symptoms you may have related to COVID-19.

Do you have any of the following?

A current diagnosis of COVID-19? [ ] Yes [ ] No

If yes, have you had a negative test result since? [ ] Yes [ ] No

A new cough [ ] Yes [ ] No

Shortness of breath or difficulty breathing [ ] Yes [ ] No

Chills [ ] Yes [ ] No

Muscle pain [ ] Yes [ ] No

Sore throat [ ] Yes [ ] No

New loss of taste or smell [ ] Yes [ ] No

**Temperature:** \_\_\_\_\_

## **Draft Telephone Screening Email**

Hello (insert potential participant name),

Thank you for your interest in the Better BP study. We are currently enrolling 660 adults to take part in this research study about how to measure blood pressure. To confirm your eligibility for this study, please respond to this email with a day and time that would work best for us to schedule your telephone screening. The screening call should take approximately 10 minutes.

Thank you again for your interest in the Better BP study.

Sincerely,

(Insert your name)

## **Better BP Screening Visit Checklist**

COVID-19 Screening     Yes     No

Symptom Tracker

Temperature Check

Consent sign and dated     Yes     No

BP cuff verified     Yes     No

Left arm \_\_

Right arm \_\_

Two Blood Pressure Measurements  Yes  No

Continue to visit 1  Yes  No

Screen fail  Yes

To be re-screen in one month  Yes  No

Date \_\_\_\_\_

Inform participants that qualify for the study that the morning of the clinic visit, participant should avoid coffee (and other caffeine containing food or beverages) smoking, exercise or eating for at least 30 minutes prior to office BP measurements.

Completed by \_\_\_\_\_

Date \_\_\_\_\_

## **Better BP Study Visit 1 Checklist**

[ ] COVID-19 Screening [ ] Yes [ ] No  
[ ] Symptom Tracker  
[ ] Temperature Check

[ ] Consent sign and dated [ ] Yes [ ] No

[ ] BP cuff verified [ ] Yes [ ] No

[ ] Vital signs done [ ] Yes [ ] No

[ ] Height and Weight

[ ] Waist and Neck circumference

[ ] Questionnaires done [ ] Yes [ ] No

[ ] Social demographic (**circle one**: email or in-person)

[ ] Pittsburg Sleep Quality Index (**circle one**: email or in-person)

[ ] State Anxiety Index (Based on randomization order)

[ ] Unattended [ ] Attended

[ ] Randomization 1

[ ] Unattended then attended

[ ] Attended then unattended

Inform participant that the morning of the clinic visit, participant should avoid coffee (and other caffeine containing food or beverages) smoking, exercise or eating for at least 30 minutes prior to office BP measurements.

Completed by \_\_\_\_\_

Date \_\_\_\_\_

# Better BP Study

## Study Visit 1 Data Collection Form

ID: \_\_\_\_\_

Date of Visit: \_\_\_\_\_

Name of tech performing visit: \_\_\_\_\_

Time of Visit: \_\_\_\_\_

### **BEFORE PARTICIPANT ARRIVES**

1. Complete symptom tracker and temperature check
2. Print consent form and all questionnaires (if not completed electronically)
3. Verify cuffs of various sizes are available:

### **AFTER PARTICIPANT ARRIVES**

4. Ask the participant if he/she needs to use the restroom prior to beginning
5. Consent participant, if not previously completed electronically
6. Measure height, weight, waist and neck circumference
  - a. Height (cm) \_\_\_\_\_
  - b. Weight (lbs) \_\_\_\_\_
  - c. Waist circumference (cm) \_\_\_\_\_
  - d. Neck circumference (cm) \_\_\_\_\_
7. Allow participants to complete the following questionnaires: Sociodemographic, Perceived Stress, and Pittsburgh Sleep Quality Index (PSQI) [if not completed electronically]
8. Measure arm circumference
  - a. Is participant right or left handed (i.e., dominant arm; circle one):  Left  Right
  - b. Arm circumference of dominant arm: \_\_\_\_\_ cm
  - c. Arm circumference of non-dominant arm: \_\_\_\_\_ cm
  - d. Is the clinic device being worn on the (**non-dominant**)? Yes  No
  - i. Reason if not worn on non-dominant \_\_\_\_\_
  - e. Put "X" next to cuff sizes that will be used

Clinic (Microlife Office AFIB)			
Cuff Size	Arm circumference	Dominant arm	Non-dominant arm
Small adult	17-21.9 cm		
Med adult	22-32 cm		
Large adult	32.1-42 cm		
Extra-large	42.1-52 cm		

9. Identify randomization assignment.

Record randomization order:

Unattended then attended

Attended then unattended

10. If the participant is randomized to unattended BP,

- a. Explain to participant the steps involved in obtaining unattended BP measurements:
  - i. You will position them and they should not move or talk
  - ii. You will start the blood pressure measurement device
  - iii. You will leave the room for 10 minutes
  - iv. After 5 minutes, they will have their blood pressure measured
  - v. They will have their blood pressure measured two more times at one minute intervals
  - vi. They should relax but not move until you return to the room
- b. Connect the BP device to the cuff
- c. Position patient for their BP measurement
- d. Start the device for a 5 minute waiting period
- e. Leave the room for 10 minutes

8. If the participant is randomized to attended BP measurements

- h. Explain to participant the steps involved in obtaining unattended BP measurements:
  - i. You will position them and they should not move or talk
  - ii. You will start the blood pressure measurement device

- iii. After 5 minutes, they will have their blood pressure measured
- iv. They will have their blood pressure measured two more times at one minute intervals
- v. They should relax but not move and there should be no talking until the three blood pressure measurements are taken
- i. Connect the BP device to the cuff
- j. Position patient for their BP measurement
- k. Start the device for a 5 minute waiting period

11. Record measurements of clinic blood pressure assessments in the order determined by randomization using the WatchBP Office AFIB device.

Attended

A)        /        /           B)        /        /           C)        /        /         
  SBP    DBP    HR            SBP    DBP    HR            SBP    DBP    HR

Unattended

A)        /        /           B)        /        /           C)        /        /         
  SBP    DBP    HR            SBP    DBP    HR            SBP    DBP    HR

**RESULTS WILL NOT BE PROVIDED TO PARTICIPANTS UNTIL THEY COMPLETE THE STUDY**

12. Schedule the participant for their next visit (visit 2). The participant should be strongly encouraged to schedule their visit for the same time the following day.

13. Answer any questions that the participant may have.

NOTES: \_\_\_\_\_

## **Better BP Study Visit 2 Checklist**

- [ ] COVID-19 Screening [ ] Yes [ ] No
- [ ] Symptom Tracker
- [ ] Temperature Check
  
- [ ] Confirm that participant has avoided caffeinated products, food, smoking, and exercise for at least 30 minutes prior to this visit.
- [ ] State Anxiety Index (Opposite of Visit 1)
  - [ ] Unattended [ ] Attended
- [ ] Clinic BP measurements: (order will be opposite of Visit 1)
  - [ ] Attended then Unattended
  - [ ] Unattended then Attended
- [ ] Randomization 2
  - [ ] ABPM device
  - [ ] HBPM device
- [ ] Actiwatch activity monitor device  
(Actiwatch device will be removed at visit 4)
- [ ] Provide participant with the assigned Device Log form
- [ ] Provide participant with State Anxiety Index for home  
(To be completed during night of monitoring)

Completed By \_\_\_\_\_

Date \_\_\_\_\_

# Better BP Study

## Study Visit 2 Data Collection Form

ID: \_\_\_\_\_

Date of Visit: \_\_\_\_\_

Name of tech performing visit: \_\_\_\_\_

Time of Visit: \_\_\_\_\_

### **BEFORE PARTICIPANT ARRIVES**

1. Verify cuff size worn at Visit 1:

### **AFTER PARTICIPANT ARRIVES**

2. Greet the participant and explain what will be done during their visit:
  - a. They will have their blood pressure measured six more times.
  - b. They will begin their 24-hour blood pressure monitoring period or asleep blood pressure monitoring
  - c. They will begin wearing an activity monitor on their wrist.
3. Ask the participant if he/she needs to use the restroom prior to beginning their measurements.
4. Identify the order for blood pressure measurement for the second visit (opposite order of visit 1).

If BP is being measured unattended:

- a. Explain to participant the steps involved in obtaining unattended BP measurements:
  - i. You will position them and they should not move or talk
  - ii. You will start the blood pressure measurement device
  - iii. You will leave the room for 10 minutes
  - iv. After 5 minutes, they will have their blood pressure measured
  - v. They will have their blood pressure measured two more times at one minute intervals
  - vi. They should relax but not move until you return to the room
- b. Connect the BP device to the cuff

- c. Position patient for their BP measurement
- d. Start the device for a 5 minute waiting period
- e. Leave the room for 10 minutes

If BP is being measured attended:

- I. Explain to participant the steps involved in obtaining unattended BP measurements:
  - i. You will position them and they should not move or talk
  - ii. You will start the blood pressure measurement device
  - iii. After 5 minutes, they will have their blood pressure measured
  - iv. They will have their blood pressure measured two more times at one minute intervals
  - v. They should relax but not move and there should be no talking until the three blood pressure measurements are taken
- m. Connect the BP device to the cuff
- n. Position patient for their BP measurement
- o. Start the device for a 5 minute waiting period

5. Record measurements of clinic blood pressure assessments in the using the WatchBP Office AFIB device.

Attended

A)        /        /           B)        /        /           C)        /        /         
 SBP    DBP    HR                    SBP    DBP    HR                    SBP    DBP    HR

Unattended

A)        /        /           B)        /        /           C)        /        /         
 SBP    DBP    HR                    SBP    DBP    HR                    SBP    DBP    HR

6. Identify randomization assignment – ambulatory blood pressure monitoring or home sleep blood pressure monitoring.

Ambulatory Blood Pressure Monitoring

Home Blood Pressure Monitoring

## **IF PARTICIPANT IS ASSIGNED THE ABPM DEVICE FIRST**

7. Ask participant what time he/she anticipates going to sleep tonight and waking up tomorrow
  - a. Anticipated time going to sleep: \_\_\_\_\_
  - b. Anticipated time waking up: \_\_\_\_\_
8. Initialize ABPM device. Serial number: \_\_\_\_\_
9. Use the participant's non-dominant arm for the WatchBP O3 ABPM.
  - a. Arm where ABPM device will be worn (**non-dominant**)? Left      Right
    - i. Reason if not worn on non-dominant \_\_\_\_\_
    - b. Put "X" next to cuff sizes that will be used

ABPM (Microlife WatchBP O3)		
Cuff Size	Arm circumference	Non-dominant arm
Small adult	17-21.9 cm	
Med adult	22-32 cm	
Large adult	32.1-42 cm	
Extra-large	42.1-52 cm	

10. Place cuff on arm
  - a. Find brachial artery (perhaps make small mark)
  - b. Arrow on cuff over brachial artery, non-latex tubing coming out of cuff top
  - c. Bottom of cuff 1" above bend/crease in elbow (if possible)
  - d. Equal tension top and bottom of cuff (1 finger easily, 2 fingers snug, top and bottom)
  - e. Wrap grey non-latex tubing around back of neck
11. Connect tubing to ABPM device (make sure it will not pull out)
12. Place the O3 device in 'Ambulatory' mode.
13. Explain to participant about importance of remaining still during readings and keeping arm a) relaxed at side or in a "sling-like" position if standing, b) resting on table, arm rest, bed, etc. if sitting/reclining
14. Take one test reading; repeat until obtain a valid reading (max 5 tries)
  - a. If cannot get a valid reading, check for cuff too loose, kink in tubing, tubing not securely connected to ABPM device; if need be, change cuff and/or ABPM device (be sure to record new serial #)
  - b. After getting a good reading, wait 30 secs, then start another reading & immediately cancel it
15. Decide if participant will use shoulder strap (preferred), Microlife belt, own belt, or jacket pocket. Instrument ABPM cover appropriately, insert ABPM in cover, and make sure participant is comfortable with this method of wearing device.
16. Review ABPM device log with participant (and remind them to bring it tomorrow or their next study visit)

17. If the participant intends to remove the device to shower/changes clothes, require the participant to practice placing the device correctly with you present.
18. Review with participant:
  - a. Importance of remaining still when BP readings are being taken
  - b. Importance of keeping arm relaxed/supported
  - c. If there is a failed reading, device will attempt three (3) retries ~1 minute apart.
  - d. If participant is consistently getting 2 failed readings, should call the study cellphone
  - e. ABPM cannot get wet
  - f. If they intend to remove the device at any point, please do so between readings
  - g. Payment depends on getting 80% successful readings

#### **IF PARTICIPANT IS ASSIGNED THE HBPM DEVICE FIRST**

19. Ask participant what time he/she anticipates going to sleep tonight and waking up tomorrow
  - a. Anticipated time going to sleep: \_\_\_\_\_
  - b. Anticipated time waking up tomorrow: \_\_\_\_\_
20. Initialize HBPM device. Serial number: \_\_\_\_\_
21. Use the participant's non-dominant arm for the WatchBP Home N.
  - a. Arm where HBPM device will be worn (**non-dominant**)?      Left      Right
    - i. Reason if not worn on non-dominant \_\_\_\_\_
  - b. Put "X" next to cuff sizes that will be used
 

HBPM (Microlife WatchBP Home N)		
Cuff Size	Arm circumference	Non-dominant arm
Small adult	17-21.9 cm	
Med adult	22-32 cm	
Large adult	32.1-42 cm	
Extra-large	42.1-52 cm	

22. Demonstrate to the participant how to place the cuff on their arm
  - a. Find brachial artery (perhaps make small mark)
  - b. Arrow on cuff over brachial artery, non-latex tubing coming out of cuff top
  - c. Bottom of cuff 1" above bend/crease in elbow (if possible)
  - d. Equal tension top and bottom of cuff (1 finger easily, 2 fingers snug, top and bottom)
  - e. Wrap grey non-latex tubing around back of neck
  - f. Connect tubing to HBPM device (make sure it will not pull out)
23. Require the participant practice placing the cuff on their arm with you present.
24. Explain to participant the importance of placing the device correctly and initializing the device when they get in bed by holding the on/off button for 3 seconds to start the initial reading and the following readings will occur 2, 3, and 4 hours after they have gone to bed.
25. Take one test reading in 'Usual' mode; repeat until obtain a valid reading (max 3 tries)

- a. If cannot get a valid reading, check for cuff too loose, kink in tubing, tubing not securely connected to H BPM device; if need be, change cuff and/or H BPM device (be sure to record new serial #)
26. Place the device in 'Nocturnal' mode.
27. Place the device in a carrier bag for the participant.
28. Review with participant:
  - a. Importance of initializing the device before going to bed by holding the on/off button for 3 seconds
  - b. If there is a failed reading, device will attempt three (3) ~1 minute apart.
  - c. If participant is consistently getting 2 failed readings while initializing the device, they should call the study cellphone
  - d. Payment depends on getting three successful readings while asleep
29. Schedule participant for their return visit (24 hours later).
30. Answer any questions that the participant may have.

NOTES: \_\_\_\_\_

\_\_\_\_\_

\_\_\_\_\_

\_\_\_\_\_

\_\_\_\_\_

\_\_\_\_\_

\_\_\_\_\_

## **Better BP Study Visit 3 Checklist**

[ ] COVID-19 Screening [ ] Yes [ ] No

[ ] Symptom Tracker

[ ] Temperature Check

[ ] Device return

[ ] Check the device for complete readings

[ ] HBPM three sleep BP readings [ ] Yes [ ] No

[ ] ABPM ~35 measurements [ ] Yes [ ] No

If No, ask participant to wear the device again to collect all necessary readings or measurements.

If yes, complete the Post Questionnaire (**circle one**: email or in-person)

[ ] Post ABPM Questionnaire

[ ] Post HBPM Questionnaire

[ ] Participant will wear the opposite monitor of Visit 2

[ ] ABPM device

[ ] HBPM device

(Actiwatch device will be remove at visit 4)

[ ] Provide participant with the assigned Device Log Form

[ ] Provide participant with State Anxiety Index for home

(To be completed during night of monitoring)

Completed by \_\_\_\_\_ Date \_\_\_\_\_

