**If at least 35 readings are NOT obtained, ask the participant to repeat the ABPM monitoring period for one night.**

**If they say yes**, clear the memory and re-initialize the device with the participant's id number and adding the text ('-2') at the end (i.e. - 1101-2). Replace the device on the participant and review the instructions again. Give the participant a new ABPM device log to complete.

**If they say no**, ask the participant to complete questions regarding the quality of sleep over the 24-hour monitoring period and the comfort of the ABPM device using the “POST ABPM QUESTIONNAIRE”.

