**If at least 2 readings are NOT obtained, ask the participant to repeat the HBPM period overnight.**

[figure not shown]
**If they say yes**, give the device back to the participant and provide them with instructions again on how to place the device and begin the readings. Also, provide them with a new HBPM device log.

**If they say no**, have the participant complete questions regarding the quality of sleep over the overnight monitoring period and the comfort of the HBPM device using the “POST HBPM QUESTIONNAIRE”.

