**It is important for us to know approximately what time you went to sleep and what time you woke up in the morning**

Time went to sleep \_\_\_\_\_:\_\_\_\_\_ AM PM (circle one)

Time woke up in the morning \_\_\_\_\_:\_\_\_\_\_ AM PM (circle one)

**It is also important that we know what times, if any, you removed the HBPM device during the night. Please record these times in the following table.**

	Time	PM/AM (circle one)	Comment (why did you remove it?)
Time removed	:	PM AM	
Time put back on	:	PM AM	
Time removed	:	PM AM	
Time put back on	:	PM AM	
Time removed	:	PM AM	
Time put back on	:	PM AM	

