Monitor interfered with normal sleeping pattern	124 (20.6)	56 (9.3)	219 (36.3)	204 (33.8)
Removed monitor due to disturbance while sleeping	23 (3.8)	23 (3.8)	16 (2.7)	541 (89.7)

**Table 9.** The relationship between attended and unattended clinic BP with left ventricular mass index (g/m^2), N=587.

Model	Unstandardized beta	Lower limit of 95% confidence intervals for beta	Upper limit of 95% confidence intervals for beta	Standard Error	t-statistic	P-value	Standardized beta
Attended clinic systolic BP	0.43	0.32	0.55	0.06	7.55	<.001	0.30
Attended clinic diastolic BP	0.42	0.24	0.60	0.09	4.66	<.001	0.19
Unattended clinic systolic BP	0.44	0.33	0.56	0.06	7.50	<.001	0.30
Unattended clinic diastolic BP	0.37	0.19	0.55	0.09	4.04	<.001	0.16

Dependent variable: left ventricular mass index (g/m^2) as continuous variable

**Table 10.** The relationship between unattended clinic BP versus awake BP on ABPM with left ventricular mass index (g/m^2), N=554

Model	Unstandardized beta	Lower limit of 95% confidence intervals for beta	Upper limit of 95% confidence intervals for beta	Standard Error	t-statistic	P-value	Standardized beta
Unattended systolic BP	0.44	0.32	0.56	0.06	7.38	<0.001	0.30
Unattended diastolic BP	0.38	0.19	0.56	0.09	3.99	<0.001	0.17
Awake systolic BP on ABPM	0.61	0.47	0.74	0.07	8.69	<0.001	0.35
Awake diastolic BP on ABPM	0.45	0.25	0.66	0.10	4.36	<0.001	0.18

Dependent variable: left ventricular mass index (g/m^2) as continuous variable

**Table 11.** The relationship between sleep BP on H BPM versus ABPM with left ventricular mass index (g/m^2), N=533

Model	Unstandardized beta	Lower limit of 95% confidence intervals for beta	Upper limit of 95% confidence intervals for beta	Standard Error	t-statistic	P-value	Standardized beta
Sleep systolic BP on H BPM	0.31	0.19	0.44	0.06	4.98	<0.001	0.21
Sleep diastolic BP on H BPM	0.23	0.05	0.40	0.09	2.54	0.01	0.11
Sleep systolic BP on ABPM	0.45	0.32	0.59	0.07	6.63	<0.001	0.28
Sleep diastolic BP on ABPM	0.36	0.16	0.55	0.10	3.64	<0.001	0.16

Dependent variable: left ventricular mass index (g/m^2) as continuous variable

**Table 12.** The relationship between attended and unattended clinic BP with urinary albumin-to-creatinine ratio (mg/g), N=555.

Model	Unstandardized beta	Lower limit of 95% confidence intervals for beta	Upper limit of 95% confidence intervals for beta	Standard Error	t-statistic	P-value	Standardized beta

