**Table 4. Domains of data collection**

1. Unattended clinic BP
2. Attended clinic BP
3. 24-hour ABPM with actigraphy
4. One night of HBPM with actigraphy
5. Questionnaires including HBPM and ABPM tolerability
6. A brief physical examination
7. Spot urine to assess albuminuria
8. Transthoracic echocardiogram

ABPM monitor and actigraph removed. Data will be downloaded onto computers dedicated to the current study. The ABPM recording will be checked for completeness. If a complete recording is not obtained, participants will be asked to repeat the ABPM procedure. Once a complete ABPM is confirmed, participants will fill out the ABPM tolerability questionnaire (**Section D.8.5**). This questionnaire will be self-administered unless participants are unable to read, in which case, it will be interviewer administered. Participants will be given an HBPM device and instructed in its use as described in **Section D.8.4.3**.

**D.6.3.2. Participants randomized to undergo HBPM then ABPM.** At Study Visit 3, participants will return the HBPM device and have the actigraph removed. Data will be downloaded onto computers dedicated to the current study and the recording will be checked for completeness. Next, participants will be asked to fill out a questionnaire on the tolerability of HBPM (**Section D.8.5**). This questionnaire will be self-administered unless participants are unable to read, in which case, it will be interviewer administered. Participants will be fitted with an ABPM device and instructed in its use as described in **Section D.8.4.2**.

**D.6.4. Study Visit 4.** Identical activities will occur at Study Visits 3 and 4 (i.e., the ABPM or HBPM devices will be returned, checked for a complete recording, and a tolerability questionnaire will be filled out). At the conclusion of Study Visit 4, participants will be escorted by study staff to the laboratory for an echocardiogram. Upon completion of the echocardiogram, participants will have successfully completed the study.

Figure 3. Activities conducted at a screening visit and the four study visits.

Screening visit	Visit 1	Visit 2	Visit 3	Visit 4

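### Participants who repeat an incomplete recording at Visit 3 are not asked to rate the failed first wear, so Hypothesis 2b can miss first-wear intolerance on either device

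*Combined protocol and SAP*

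**What the plan says.** The documents route the questionnaire in different ways.

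- **Visit 3 Checklist.** Complete recording: "If yes, complete the Post Questionnaire". Incomplete recording: "If No, ask participant to wear the device again to collect all necessary readings or measurements", with no questionnaire on that branch. The Visit 3 Data Collection Form makes the same split (items 1–3 for HBPM first, items 17–19 for ABPM first).
- **ABPM download procedure.** Below 35 readings the coordinator must "ask the participant to repeat the ABPM monitoring period for one night". A participant who agrees has the device memory cleared, is refitted and gets a new log. One who declines is still rated: the coordinator is to "ask the participant to complete questions regarding the quality of sleep over the 24-hour monitoring period and the comfort of the ABPM device".
- **HBPM download procedure.** The same structure below two readings: "ask the participant to repeat the HBPM period overnight", with a new log if the answer is yes and the questionnaire if it is no.
- **Research plan, D.6.3.1 (ABPM first).** "Once a complete ABPM is confirmed, participants will fill out the ABPM tolerability questionnaire". D.6.3.2 (HBPM first) places the form after the completeness check but does not require a complete recording.
- **Visit 4.** The Checklist again ties the forms to the yes branch. Item 36 of the Visit 4 Data Collection Form asks for the questionnaire unconditionally.

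D.11.5.2 tests Hypothesis 2b from questionnaire responses, with McNemar tests for pain, skin irritation and bruising. SAP item 6 tabulates the items in Table 8, including "Removed monitor due to disturbance while sleeping". Neither says which wear is meant when there were two. The device logs record removals for each wear (the HBPM log states "It is also important that we know what times, if any, you removed the HBPM device during the night"), but neither analysis section uses them.

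**The concern.** Night-time removal is a tolerability outcome and also a cause of a failed recording. If the rating waits for a successful recording, the measurement is conditioned on something the outcome influences. A participant who pulled the cuff off on the first night, agreed to repeat and managed the second night would be rated once, after the better night.

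The decline branch protects only those who refuse. The Visit 2 and Visit 3 forms have staff tell participants that payment depends on obtaining enough successful readings, which encourages acceptance. The REDCap instrument list shows one post-ABPM and one post-HBPM form per record, with no stated place for a second wear.

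At stake is the claim in Hypothesis 2b that HBPM is better tolerated, above all on removal and sleep disturbance.

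**Working it through.** **1. The plan's own figure.** D.12.2.2 gives a detectable difference of 3 points (25% v 22%) with n = 600, 80% power and discordant rates of 5% (ABPM only) and 2% (HBPM only). By the McNemar normal approximation, with d = 0.03 and p_d = 0.07:

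power = Φ[(d√n − 1.96√p_d) / √(p_d − d²)] = Φ[(0.7348 − 0.5186) / 0.2629] = Φ(0.823) = 79.5%.

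The n for 80% power is 609. The figure reproduces.

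**2. What lost ratings would do.** The documents give no repeat count, so the shares below are assumptions. Suppose a share of the poor-tolerance cases on one device is re-rated as tolerant after a repeat, with the cut-point held fixed:

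| Share lost | ABPM-only cases lost: difference, power | HBPM-only cases lost: difference, apparent power |
|---|---|---|
| 10% | 2.5 points, 67.2% | 3.2 points, 85.4% |
| 20% | 2.0 points, 51.6% | 3.4 points, 90.2% |
| 30% | 1.5 points, 34.7% | 3.6 points, 93.8% |
| 50% | 0.5 points, 8.3% | 4.0 points, 98.1% |

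Losing ABPM intolerance works against Hypothesis 2b; losing HBPM intolerance works for it.

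**3. Can the device rules fix the direction?** ABPM plans 48 readings at 30-minute intervals (D.10.4). The field check is 35, so 48 − 35 = 13 readings, or 6.5 h, may be missed, but only if every other reading is valid. The three sleep examples in the manual's buffer section each last 7 h, or 14 readings. Removal for the whole night leaves 48 − 14 = 34, which fails. Under the 39-reading rule in D.10.4 the allowance is 9 readings, or 4.5 h.

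HBPM reads at 2, 3 and 4 h. Removal before the 3 h reading fails a two-reading rule, and removal before the 4 h reading fails a three-reading rule. The documents use both rules: three in the Summary and the Visit 3 Checklist; two in the HBPM download procedure, the Visit 3 form and the Visit 4 documents. Removal can therefore fail the check on either device, and who is sent to repeat is itself unclear.

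**4. Table 8 as reported (N = 603).** McNemar chi-square = (b − c)² / (b + c), where b is ABPM only and c is HBPM only.

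- *Removed while sleeping:* 23 v 23, p = 1.0. Each device has 23 + 16 = 39 removers (6.5%). Adding 16 ABPM-only removers gives 16² / 62 = 4.13, p = 0.042; by symmetry, 16 more HBPM-only removers give the same p in the other direction. Ten more HBPM-only removers (23 v 33) give 100 / 56 = 1.79, p ≈ 0.18. If 5 to 20 removers per device had been missed (an assumption), the rate would be 44/603 = 7.3% to 59/603 = 9.8%.
- *Pain:* 160 v 37. About 90 more HBPM-only cases, moved from neither, are needed to lose p ≤ 0.05.
- *Bruising:* 84 v 19. About 42 more are needed.
- *Interfered with sleep:* 124 v 56. About 39 more are needed.
- *Uncomfortable to wear:* 109 v 68. About 14 more are needed, so this row is less secure.

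**5. Was the form in practice limited to complete recordings?** All 12 rows of Table 8 sum to 603. Complete ABPM plus clinic data exist for 569 (Table 2), and complete sleep data on both devices for 547 (Table 7). So 603 − 569 = 34 (5.6%) and 603 − 547 = 56 (9.3%) lie outside those sets but inside Table 8. This suggests that questionnaires were not limited to complete recordings. It is not proof: missing answers could have been coded as not occurring, and complete for analysis may differ from the field check.

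**The case against.** A reader might infer that the questionnaire is given only after an acceptable recording and that the rule erases intolerance. The documents do not support that. Decliners are rated on the failed wear, Visit 4 item 36 is unconditional, and the visit overview and task lists attach no completeness condition. For devices picked up or mailed back, staff check for enough readings and for a completed post-ABPM questionnaire together. The removal items do not restrict the answer to the latest wear, so a repeater could report the earlier removal. Table 8 still shows 39 removers per device. All of this stands and limits the point to participants who accept a repeat.

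A reader might also infer that the rule favours HBPM, because ABPM seems to tolerate hours of removal while HBPM does not. That depends on no other ABPM reading failing, and a full night off fails ABPM anyway. The contrast between D.6.3.1 and D.6.3.2 is confined to the research plan, which names different devices from the manual; the manual's download procedures treat both devices alike.

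Finally, a failed recording may be a reading error rather than intolerance, and the tables are already filled, so new visit procedures cannot alter these data. Both are fair. They bear on size and remedy, and do not supply the missing rule on which wear is rated.

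**Conclusion.** The gap is real and limited. At Visit 3, for participants who accept a repeat, nothing calls for a rating of the failed wear, and nothing in D.11.5.2 or SAP item 6 says which wear counts. First-wear intolerance can be missed on either device. Size and net direction cannot be determined without the number of repeats per device and the reasons for failure; every shift shown above is an assumption.

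The removal row is the most exposed, because the event it counts can cause the failed recording and its discordant counts are tied. The pain and bruising contrasts, both named in Hypothesis 2b, are robust to any plausible loss of this kind. The documents do not support a conclusion that the tolerability result as a whole is invalid or tilted towards HBPM. This is a cheap improvement to measurement and reporting.

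**What to change.** 1. Reconcile the ABPM and HBPM download procedures, the Visit 3 and Visit 4 Checklists, the Visit 3 and Visit 4 Data Collection Forms and D.6.3.1/D.6.3.2, so that the post-ABPM or post-HBPM questionnaire is completed at the first return of each device, before any repeat wear.
2. Add to SAP item 6 that Table 8 uses the first wear of each device, and that any questionnaire from a repeat wear is stored and reported separately.
3. For data already collected, report the number of repeats per device. As a sensitivity analysis only, recode night removal from the first-wear logs, where they survive, counting removals within the sleep period whose recorded reason is disturbance or discomfort. It should not replace the main table: it would use logs for repeaters and questionnaires for everyone else, and the logs also record removals for other reasons, such as showering.

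The cost is one existing short form completed earlier, with the few repeaters possibly filling it in twice, plus one SAP sentence, a count, and a recode from logs that participants were asked to return.
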